7. RESULTS

Table 4 Disposition of patients

Patients enrolled	
Received at least one cycle of study treatment	
Evaluable patients	
End of study (evaluable population)	
Death	
Lost to follow-up	
Censored at database closure	
Study completion (24 months of follow-up after PD)	

Table 5 Protocol deviations

Deviation type	Total
Informed consent form	
Efficacy criteria	
Eligibility criteria	
Incorrect dosing regimen	
Other	
Safety	

Table 6. Baseline characteristics by biomarker

	wtBRAF (n=161)	Mutant BRAF (n=20)	p-value*	wtPI3K and PTEN >3 (n=69)	Mutant PI3K or PTEN ≤3 (n=98)	p value*	Non-DP (n=158)	DP (n=23)	p value*
Female									
Mean age (SD)									
Primary location									
Ascending colon									
Transverse colon									
Descending colon									
Sigmoid colon									
Rectum									
Stage									
I									
II									
III									
IV									
Surgery of the primary tumour									
Performance status									
0									
1									
2									
Number of metastatic organs									
0									
1									
2									
3									
4+									
Liver metastasis									
0									
≤3, ≤5 cm									
>3 or >5 cm									
Node metastases¹									
Lung metastases¹									
Peritoneal metastases¹									

Patients with only resectable liver metastases ²									
Chemotherapy									
FOLFOX+Cetuximab									
FOLFIRI+Cetuximab									
Mean Leucocytes (SD)									
Mean Haemoglobin (SD)									
Mean Platelets (SD)									
Mean ALP (SD)									
LDH >450									
Mean CEA (SD)									

¹

- Fisher's exact test for categorical variables and Wilcoxon rank-sum test for ordinal or continuous data

² Missing in one patient The patient does not have metastasis in any other location, and those in the liver are ≤ 3 in number and ≤ 5 cm in size.

Table 7. MEASUREMENTS OF TREATMENT COMPLIANCE

	Total (n=)
Treatment disposition	
Received at least one injection (safety population)	
Efficacy population	
Received at least 12 cycles of cetuximab	
Received at least 12 cycles of chemotherapy+cetuximab	
Received less than 12 cycles of cetuximab	
Received 3 or less administrations of combination	
FOLFOX+cetuximab	
FOLFIRI+cetuximab	
End of Treatment (EOT)	
Reasons for end of treatment	
PD	
PI decision (24 due to surgery, 2 radiotherapy, 2 complete response, 49 others)	

Patient decision	
Toxicity (related to treatment)	
AE (unrelated to treatment)	
No data of EOT available	

Table 8: Patients excluded from the efficacy or safety analysis

Pat. #	Hospital	Reason for exclusion from efficacy analysis	Valid for safety

Table 9. Response Rates (efficacy population) based on BRAF status

Best Response	N= all patients (%)	N= wt-BRAF (%)	N= mutant-BRAF (%)
Complete response (CR)			
Partial response (PR)			
Stable disease (SD)			
Disease Progression (PD)			
Not evaluable (NE)			
Overall response			
Disease Control Rate			

Figure 1. Progression free-survival

Progression free survival (PFS) based on the analysis of X patients showed a median of X (95% CI: X - X) months.

Figure 2. Overall survival

When OS was evaluated, an estimated median of X (95% CI: X - X months was reported.

The median OS of wt-BRAF patients was X (95% CI: X - X) months and for that of mutant BRAF patients was X (95% CI: X - X months (adjusted HR:X, CI 95% X- X; p-value=X).

Table 10. General toxicity profile (AEs+SAEs+SUSARs)

Adverse event	Any grade	Grade 3	Grade 4	Grade 5
	N (%)	N (%)	N (%)	N (%)

Table 12. Toxicity profile post treatment beginning (AEs+SAEs+SUSARs)

Adverse event	Any grade	Grade 3	Grade 4	Grade 5
	N (%)	N (%)	N (%)	N (%)

Table 13. Toxicity profile post treatment beginning related to treatment (AEs+SAEs+SUSARs)

Adverse event	Any grade	Grade 3	Grade 4	Grade 5
	N (%)	N (%)	N (%)	N (%)

Table 14. Toxicity profile post treatment beginning related to treatment with Cetuximab (AEs+SAEs+SUSARs)

Adverse event	Any grade	Grade 3	Grade 4	Grade 5
	N (%)	N (%)	N (%)	N (%)

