Statistical methods	
Sample size considerations
 
Initially, the number of patients required to be recruited in 24 months was 155 and the total study duration (recruitment + follow-up) was considered to be 28 months for 115 events to occur. After recruiting 157 patients, it was determined that about 70 of these patients had insufficient samples for biomarker analysis preventing their inclusion in the analysis of the primary objective. Therefore, in order to reach the 115 events necessary to evaluate the primary endpoint, the total number of patients to be included in the trial was increased up to 240. Finally, 221 patients were considered sufficient to observe the required number of events. After central reviewing and monitoring, 181 patients with wt-RAS were finally included for efficacy analysis.
 
For sample size calculation, it was assumed that patients could be classified into 2 groups based on their clinical characteristics and their biomarker profile. The log-rank method was planned to be used for the comparison of PFS during follow-up between the two groups. A minimum difference in PFS of 20% (50% vs 30%) was expected between the groups at 12 months, given the following assumptions:
 
 • Alpha error (two-tailed): 5% • Beta error: 20% 
Statistical considerations
 
The primary and the secondary efficacy objectives were analysed using per-protocol analysis. Patients fulfilling all eligibility criteria and with documented wt-RAS status (KRAS and NRAS) were included in the efficacy analysis.
 
Efficacy analysis was based on radiological imaging performed throughout the study and assessed by site investigators. Any finding considered as non-evaluable by the investigator was excluded from the analysis (it was considered as non-existent).
 
For continuous variables, mean, standard error (for efficacy variables), standard deviation (for other measurements), median, 25th percentile, 75th percentile, minimum and maximum, were considered. Categorical variables are presented using frequencies and percentages.
 
The 95% two-sided confidence intervals (CI 95%) of Kaplan–Meier

---------------------	---

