	
quartiles were calculated according to Brookmeyer and Crowley methods (55,56). Safety data were analysed throughout the entire study.
 
In the first step to develop a prediction model for PFS, univariate Cox regression analysis including all clinical variables collected in the study was performed in order to identify which should be considered for the model selection thereafter in the second step. All factors with a ≤ 0.15 p value (Appendix 15.2, item 4) were selected for the multivariable Cox analysis. The cut-off of ≤ 0.15 p-value was used in order to include the presence of resectable liver metastases as that is a well-known prognostic factor in mCRC. In the second step multivariable Cox regression analysis was performed including those variables identified in the univariate analysis. Importantly, the variable treatment (FOLFIRI vs FOLFOX) was not included for the development of the prediction score because it was not a characteristic intrinsic to the patients.

--	--

12-MONTHS PFS RISK MODEL DEFINITION

Clinical variables and biomarkers were used to build a score to predict 12-months PFS, by using a multivariable Cox regression model built with those clinical variables with a $p \leq 0.15$ in the multivariable analysis (performance status, chemotherapy regimen, sidedness, resectable only liver metastases). Once the first risk score was built adding up the coefficients of the multivariable model ($PS > 0 = 0.6$, left sided = -0.5, resectable liver only metastases = -0.4 and folfiri+cetuximab therapy = Not evaluable), ROC curves were computed for PFS at 12 months using a logistic regression model. All 4 scores (A. Clinical variables including PS, sidedness and resectable only liver metastases, B. Clinical variables + BRAF mutation; C. Clinical variables + PI3K mutation or PTEN ≤ 3 ; D. Clinical variables + DP) had comparable low areas under the curve, ranging between 0.5 and 0.7, overall: The AUC of the score containing the clinical variables was 0.67 (95% CI) (0.60-0.75).

The AUC of the score with clinical variables and BRAF mutational status was 0.68 (0.61-0.75, p-value = 0.37). The AUC of the score with clinical variables and PI3KCA mutation/PTEN status was 0.69 (0.61-0.76, p-value = 0.32). The AUC of the score with clinical variables and DP phenotype was 0.66 (0.58-0.73, p-value = 0.09).

SAFETY RESULTS

CONCLUSIONS

DATE OF THE REPORT:

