6.5.1.3. Analysis population

Efficacy variables were analysed in all subjects who provided their informed consents, were included in the trial and did not present significant protocol deviations throughout the study period.

An intention-to-treat analysis in all patient enrolled into the study was not performed because the primary study objective was to evaluate the predictive value of the three biomarker BRAF, IGF-1RP/MMP-7 (Double-positive Phenotype/DP) and PI3K-PTEN on PFS in wt-RAS CRC patients receiving standard chemotherapy plus bi-weekly cetuximab as first-line therapy, but patients with significant protocol deviations (e.g. RAS mutations, missing biomarker data and those not receiving cetuximab treatment) could not contribute to the investigation of the primary objective.

All patients who received study medication were included in the safety analysis. .

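### PI3K-PTEN status is known for only 167 of the 181 efficacy patients, and the SAP does not say which patients lie behind the clinical AUC of 0.67 printed beside the PI3K-PTEN score's 0.69

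*SAP*

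**What the plan says.** **Analysis set.** The SAP Synopsis (Statistical methods) states that "181 patients with wt-RAS were finally included for efficacy analysis". It defines that set by eligibility and documented wild-type RAS, without mentioning marker availability. The Methodology row of the Synopsis says that 181 patients were evaluated for BRAF, PI3K and PTEN as well as RAS. SAP 6.5.1.3 explains the absence of an intention-to-treat analysis on the ground that "patients with significant protocol deviations (e.g. RAS mutations, missing biomarker data and those not receiving cetuximab treatment) could not contribute" to the primary objective.

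**Marker counts.** The column heads of Table 6 (SAP 7) give 161 wild-type BRAF and "Mutant BRAF (n=20"), 158 non-DP and 23 DP, but "wtPI3K and PTEN >3 (n=69") and "Mutant PI3K or PTEN ≤3 (n=98").

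**Primary comparison.** SAP 6.5.1.1 sets the AUC of the clinical score against the AUC of the clinical score plus each marker. In SAP 6.5.1.5, step 2 sums the coefficients of the factors a patient has, and an absent factor adds 0. Step 5 repeats the scoring with each marker, step 6 compares the four scores, and step 7 picks the most suitable one. No step says what to do with an unknown marker or requires a common set of patients.

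**Printed results.** The Synopsis reports "The AUC of the score containing the clinical variables was 0.67 (95% CI) (0.60-0.75") and "The AUC of the score with clinical variables and BRAF mutational status was 0.68 (0.61-0.75, p-value = 0.37"). The PI3K-PTEN score has 0.69 (0.61-0.76, p = 0.32) and the DP score 0.66 (0.58-0.73, p = 0.09). No AUC carries an N. The text describes the four as comparable and low.

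**The concern.** The added value of a marker is the difference between two correlated AUCs, and that difference is interpretable only if both are computed in the same patients. PI3K-PTEN is the one marker with unclassified patients, and its score has the highest AUC of the four. If 0.67 comes from 181 patients and 0.69 from 167, part of the 0.02 may reflect who was left out. If the 14 were kept and scored 0, unknown status was treated as non-activated. If all four scores were run on 167, then 181 is not the N of the primary comparison. The text allows each of these.

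The stated rule and the stated set also disagree: read literally, 6.5.1.3 puts the 14 outside the primary objective, yet they are counted in the 181. What is at stake is the size of the PI3K-PTEN increment and the step 7 choice of score.

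**Working it through.** **1. Counts (Table 6 against the Synopsis)**

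| Marker | Sum | Difference from 181 |
|---|---|---|
| BRAF | 161 + 20 = 181 | 0 |
| DP | 158 + 23 = 181 | 0 |
| PI3K-PTEN | 69 + 98 = 167 | 14 (14/181 = 7.7%) |

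BRAF and DP reproduce the stated efficacy set; PI3K-PTEN does not.

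**2. Can the printed intervals reveal the N?** The printed clinical interval implies SE = (0.75 - 0.60)/3.92 = 0.038. The Hanley-McNeil formula is SE² = [A(1-A) + (n1-1)(Q1-A²) + (n0-1)(Q2-A²)]/(n1·n0), with Q1 = A/(2-A) and Q2 = 2A²/(1+A). The documents do not give the share of patients with progression or death by 12 months, so 40-60% is assumed. With A = 0.67:

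- N = 181: SE 0.040 to 0.042, interval about 0.59 to 0.75
- N = 167: SE 0.042 to 0.043, interval about 0.59 to 0.75

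The printed interval is reproduced to about 0.01, but 181 and 167 cannot be told apart.

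**3. Does p = 0.32 look paired?** The displayed difference is 0.69 - 0.67 = 0.02 (0.01 to 0.03 allowing for rounding).

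- Implied SE: z for a two-sided p of 0.32 is 0.994, and 0.02/0.994 = 0.020 (0.010 to 0.030 with rounding).
- If the AUCs were independent: SE = √2 × 0.0383 = 0.054, z = 0.02/0.054 = 0.37, p = 0.71.

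The printed p fits a paired test. Such a test could have been run in the 167 with a matched clinical AUC that is not printed, or in all 181 with the unknowns scored 0. It does not tell us which.

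**4. How far could the clinical AUC move if 14 patients are lost at random?** There are no patient data, so this is a simulation on assumptions:

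- Score weights from the Synopsis: 0.6 for PS>0, -0.5 for left-sided, -0.4 for resectable liver-only disease.
- Assumed prevalences of 50%, 70% and 15%; logistic outcome with slope 1.6 on the centred score; 12-month event share of 40%, 50% or 60%.
- Data sets of 181 were kept if the full-sample AUC lay between 0.665 and 0.675 (147 to 163 per event share), with 40 random deletions of 14 in each. Weights were not refitted after deletion.

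| Quantity | Result over the three event shares |
|---|---|
| SD of the shift | 0.011 to 0.012 |
| Central 95% range | about -0.02 to +0.02 |
| Rise of at least 0.01 | about 19% |
| Rise of at least 0.02 | about 4-5% |

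Only a rise counts, because the clinical AUC in the 167 would have to be higher than 0.67 to absorb the displayed difference. Counting shifts of 0.02 or more in either direction gives about 7-8%, which overstates the risk. Removing the 14 patients least, or most, in line with the score moves the AUC by about +0.09 or -0.055. These are extremes under selective loss, not forecasts.

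**The case against.** A reader might infer that 0.67 in 181 patients was the comparator actually tested against 0.69 in 167, and that the PI3K-PTEN gain is therefore an artefact. The documents do not support that. They show one clinical AUC printed, not which one was tested, and the p-value points to a paired test. If the clinical AUC was matched but not printed, the p-value stands and only the displayed 0.67 is the wrong companion to 0.69. Even under random loss of patients, a rise that would absorb the full 0.02 is uncommon.

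It is also fair to say that the SAP claims no gain. If patient mix explained part of the 0.02, the negative reading would hold more firmly.

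The conflict with 6.5.1.3 can be softened. Missing biomarker data may there mean no usable sample, as for the roughly 70 patients in 6.5.2. A composite of two assays can be unclassifiable when one of them fails, even in a patient who was tested. The documents do not say why the 14 are unclassified, so selective loss is a possibility only.

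Finally, the Table 6 counts are not ROC denominators. The SAP does not say how patients censored before 12 months enter the logistic model, so 181 and 167 are upper limits for complete-case sets.

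All of this narrows the point. It does not supply the missing N, the rule for an unknown marker or the matched clinical AUC.

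**Conclusion.** The point holds as a gap in the primary comparison. Fourteen of 181 efficacy patients (7.7%) have no PI3K-PTEN category. This conflicts with 6.5.1.3 as written and sits poorly with the Synopsis statement that 181 were evaluated for PI3K and PTEN. The displayed 0.02 cannot be confirmed as a same-patient difference with marker status known. Random loss alone would move the clinical AUC with an SD of about 0.011, rising by at least 0.01 in about 19% and at least 0.02 in about 4-5% of cases. Those figures rest on the assumed prevalences, outcome model and 12-month event share of 40-60%.

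The conclusion that the four AUCs are comparable and low is not overturned, and p = 0.32 is not shown to be wrong. What remains uncertain is the size of the PI3K-PTEN increment and the step 7 choice among the scores.

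**What to change.** 1. For each marker, fit the clinical and the clinical-plus-marker score in the same patients: those with that marker known and with 12-month PFS status determinable. Compare the two AUCs with a paired method.
2. Print the matched clinical AUC, with N and events, beside each marker AUC.
3. Make the step 7 choice among all four scores on one common set with every marker known.
4. State that a missing marker is not scored as 0, and say how PI3K-PTEN is classified when only one of its two components is available.
5. Reconcile the Synopsis (Methodology and Statistical methods), 6.5.1.3 and Table 6 on which patients form the set for each marker, and state how early censoring is handled.

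The cost is a few extra model fits, some SAP wording, and a slightly smaller N for PI3K-PTEN (at most 167) and for the common set. No new data are needed. If the matched clinical AUC is again 0.67, the displayed comparison is confirmed; if not, the reported increment needs correcting.

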6.4 Treatment assignment

The selection of treatment between FOLFOX-6 (m) + biweekly cetuximab or FOLFIRI (m) + biweekly cetuximab will be made by the Principal Investigator, according to the usual clinical practice of his center.

Single-arm, multicenter, prospective phase II clinical trial for biomarker validation in patients with advanced and / or metastatic colorectal cancer with non-mutated KRAS gene treated with chemotherapy plus biweekly cetuximab as first-line therapy

After confirmation of eligibility, the center's staff will fax an inclusion request form to the Sponsor (GEMCAD Technical Secretariat [REDACTED]) in which they must record the treatment chosen by the Principal Investigator for the patient.

The GEMCAD Technical Secretariat will return a communication to the center to confirm that a new patient has been registered in the study.

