7.1.5. Warnings and precautions

Respiratory disorders

Individual cases of interstitial lung disease have been reported in which the causal relationship with cetuximab is unknown. If interstitial lung disease is diagnosed, cetuximab should be discontinued and the patient treated appropriately.

Skin reactions

If a patient develops a severe skin reaction (grade ≥ 3 ; US National Cancer Institute - Common Toxicity Criteria, NCI-CTC, v3.0), cetuximab treatment should be discontinued. Treatment can be resumed only if the reaction subsides to grade 2 (see section 4.8 of the product data sheet).

If the severe skin reaction has occurred for the first time, treatment can be resumed without change in dose.

If severe skin reactions occur for the second or third time, cetuximab should be stopped again. Treatment can be resumed at a lower dose (400 mg / m^2 after the second time, and 300 mg / m^2 after the third time) only if the reaction has subsided to grade 2.

If severe skin reactions appear for the fourth time, or they do not subside to grade 2 during treatment interruption, permanent discontinuation of cetuximab treatment is required.

Single-arm, multicenter, prospective phase II clinical trial for biomarker validation in patients with advanced and / or metastatic colorectal cancer with non-mutated KRAS gene treated with chemotherapy plus biweekly cetuximab as first-line therapy

Electrolyte disturbances

Progressive decreases in serum magnesium levels occur frequently, which can lead to severe hypomagnesemia. Hypomagnesemia is reversible after stopping cetuximab treatment. In addition, hypokalemia may occur as a result of diarrhea.

Hypocalcemia can also occur; in particular the frequency of severe hypocalcaemia may be increased when used in combination with platinum-based chemotherapy.

Serum electrolyte level determinations should be performed prior to treatment and periodically during treatment with cetuximab. Electrolyte replenishment is recommended as needed.

Neutropenia and related infectious complications

Patients receiving cetuximab in combination with platinum-based chemotherapy are at increased risk of severe neutropenia, which can lead to later infectious complications such as febrile neutropenia, pneumonia, or sepsis. Close monitoring is recommended in these patients, especially in those with skin lesions, mucositis or diarrhea, which may facilitate the development of infections (see section 4.8 of the product data sheet).

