4.1.1. CRC treatment

Historically, the median survival rate of patients with metastatic disease has been 11–13 months after treatment with a combination of the fluoropyrimidine, 5-fluorouracil (5-FU), and leucovorin (LV) (8). The introduction of oxaliplatin and irinotecan in advanced colorectal chemotherapy has improved the frequency and extent of clinical response compared with that achieved with 5-FU/LV alone, and it has enhanced progression free survival (PFS) and overall survival (OS). Current research is focused on optimising this systemic chemotherapeutic regimen.

Irinotecan, a specific DNA topoisomerase I inhibitor, has shown significant activity as a single agent in the treatment of patients with CRC refractory to 5-FU (9,10). Furthermore, the addition of irinotecan to the combination therapy with 5-FU/LV (FOLFIRI regimen) significantly improves OS, response rate, and time until progression in the therapy of previously untreated mCRC compared to 5-FU/LV alone (11).

Oxaliplatin, a platinum analogue, causes the inter- and intra-strand cross-linking of DNA, thereby preventing DNA replication. It is effective and well tolerated when administered with LV as a bolus and an infusion (FOLFOX regimen); however, neutropenia and sensory neuropathies are more frequent with this combination than with treatment with 5-FU and LV alone (12,13,14,15,16). In recent years there has been significant progress in the treatment of mCRC, which has resulted in the improvement of patient life expectancy.

Therapies targeted against vascular endothelial growth factor receptor and epidermal growth factor receptor (EGFr) have been recently established in mCRC treatment.

It has been proved that targeted therapies, specifically designed to inhibit carcinogenic biochemical processes, are effective in the treatment of mCRC. Cetuximab (Erbitux®), a chimeric monoclonal antibody targeted against EGFr, has been approved by the FDA for use in combination with irinotecan for the treatment of EGFr-expressing mCRC in patients who are refractory to irinotecan-based chemotherapy. It has also been approved as a single agent for the treatment of EGFr-expressing recurrent mCRC in patients who are intolerant to irinotecan-based chemotherapy (17,18,19,20). Within the European Union (Erbitux® SmPC), cetuximab is indicated for the treatment of EGFr-expressing wt-RAS mCRC:

- in combination with irinotecan-based chemotherapy,
- as first-line therapy in combination with FOLFOX,

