At the time of trial initiation, there was no published information on the usage of the bi weekly cetuximab regimen in combination with oxaliplatin (FOLFOX-6); however, there were several ongoing clinical trials to evaluate this treatment regimen. Experience gathered from daily clinical practice at some hospitals suggested a benefit of the bi weekly regimen over the weekly administration schedule, indicating that it is more convenient for patients and allows health systems to save resources. Therefore, the sponsor in this study ultimately left the choice of FOLFOX or FOLFIRI treatment to the principal investigators (PIs) at each centre, according to their own experience in the

treatment of the condition. There are prior data on the efficacy of the combination of oxaliplatin with cetuximab-based regimens, and no difference among oxaliplatin regimens has been reported. Moreover, the added convenience of combining the FOLFOX-6 regimen with the bi-weekly administration schedule justifies its use in this study.

After demonstrating differences in clinical benefits obtained with bi-weekly cetuximab treatment among mCRC patients, considering KRAS mutational status, it was justified to conduct a clinical trial with the secondary objective of evaluating the cetuximab toxicity profile when administered as a bi-weekly regimen.

Justification of the investigational biomarkers

Biomarker evaluation constitutes one of the fundamental development fields at GEMCAD. Biomarkers currently play an important role in the detection and treatment of patients with CRC. Biomarkers also direct diagnostic and treatment modalities by facilitating the selection of therapeutic drugs across a broad spectrum of patients. There are attempts to personalise chemotherapy based on the presence or absence of specific biomarkers. Therefore, the design of the trial, from the very beginning, included the primary endpoint to identify the potential role of relevant biomarkers in patient characterisation and treatment selection.

Role of insulin growth factor receptor (IGFr) pathway in mCRC

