6.5.1.4. Covariate analysis

The following baseline characteristics were studied by biomarkers in order to properly categorise the sample:

- Gender
- Age
- Primary Tumour location and sidedness (ascending colon, transverse colon, descending colon, sigma and rectum)
- Stage of the disease
- Surgery of the primary tumor
- ECOG Performance Status
- Number of metastatic organs
- Specific locations of metastasis including number, size and location node, lung, peritoneal and liver (considering also those patients with only resectable liver metastases for comparison)
- Mean values of haematological tests including leucocytes, haemoglobin, platelets,.
- Baseline LDH levels >450

- Mean ALP and Mean CEA
- Chemotherapy (FOLFOX+Cetuximab /FOLFIRI+Cetuximab)

These groups have been used for univariate and multivariable analysis in order to evaluate efficacy variables such as ORR and PFS. Disease response was clinically assessed by the investigator based on the radiological imaging data collected throughout the study. Any finding considered as non-assessable by the investigator was excluded from the analysis (it was considered as non-existent).

For continuous variables, mean, standard error (for efficacy variables), standard deviation (for other measurements), median, 25th percentile, 75th percentile, minimum and maximum, were evaluated. Categorical variables were presented using frequencies and percentages.

The 95% two-sided confidence intervals (95%CIs) of Kaplan–Meier quartiles for time to event variables were calculated according to Brookmeyer and Crowley methods (Brookmeyer, 1982). The 95% two-sided CIs for the Kaplan–Meier estimates at various time points were calculated according to the methods described by Collett (Collett, 1992).

Safety data were analysed throughout the entire study and presented by descriptive analysis.

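### The SAP's safety tables do not separate FOLFOX6 from FOLFIRI, so a harm confined to study oxaliplatin is under-reported for the patients who received it

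*SAP*

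**What the plan says.** SAP section 7 shows four adverse-event shells: "Table 10. General toxicity profile (AEs+SAEs+SUSARs", two further tables (12 and 13) for events after the start of treatment and for treatment-related events, and "Table 14. Toxicity profile post treatment beginning related to treatment with Cetuximab (AEs+SAEs+SUSARs". All four have the same columns: any grade, grade 3, grade 4 and grade 5. None has a column for chemotherapy regimen. The numbering skips Table 11, so that table cannot be judged.

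On the population, SAP 6.5.1.3 states: "All patients who received study medication were included in the safety analysis". On the method, SAP 6.5.1.4 states: "Safety data were analysed throughout the entire study and presented by descriptive analysis". That section lists chemotherapy regimen among the covariates, but applies those groups to efficacy variables such as response and PFS. SAP 6.5.1.2 defines the safety endpoint as adverse events related to the combination treatment.

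There are two combinations. Under Protocol 6.4 the choice between FOLFOX6 and FOLFIRI "will be made by the Principal Investigator, according to the usual clinical practice of his center". The study description at the front of the SAP evaluates the feasibility of biweekly cetuximab with FOLFOX or FOLFIRI, and reported toxicities are one of its measures. SAP 4.2 adds that when the trial began "there was no published information on the usage of the bi weekly cetuximab regimen in combination with oxaliplatin (FOLFOX-6".

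**The concern.** A single pooled column describes a mixture of two regimens whose proportions were set by site habit. Where a harm belongs to a drug in only one regimen, patients who were never given that drug in the study still count in the denominator.

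Oxaliplatin neurotoxicity is the clear case. Protocol 7.2.3 has a dedicated dose-modification table for it, and the FOLFIRI section has no counterpart. SAP 4.1.1 says of FOLFOX that "neutropenia and sensory neuropathies are more frequent with this combination than with treatment with 5-FU and LV alone".

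At stake is the toxicity picture for the combination that had the least prior evidence. The biweekly studies described in Protocol 4.3 that name a chemotherapy partner all used irinotecan. A reader who wants the neurotoxicity rate for biweekly cetuximab with FOLFOX6 will not find it in the tables shown, and will read a lower figure in its place.

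**Working it through.** The safety shells are empty, so there is no figure in the plan to reproduce. The check is of direction and possible size.

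**Inputs**
- Column layout: SAP section 7, Tables 10, 12, 13 and 14.
- Denominator: everyone treated (SAP 6.5.1.3). The number is blank; the 221 recruited (SAP 6.5.2) is taken as an upper bound.
- FOLFOX share of treated patients, *w*: not given. Assumed 0.3, 0.5 and 0.7.
- Event rates on FOLFOX (*rF*) and FOLFIRI (*rI*): not given. Assumed values are shown below. The 6% is borrowed from the 70-patient study of biweekly cetuximab with irinotecan cited in Protocol 4.3, which reported 6% grade 3 and 4 neutropenia.

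**Formula:** pooled rate = *w* × *rF* + (1 − *w*) × *rI*.

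**Step 1: a harm confined to study oxaliplatin.** Here *rI* = 0, so pooled rate = *w* × *rF*. For any share below 100% this is less than *rF*. The direction is arithmetic; only the size needs assumptions. With *rF* = 15%: 0.3 × 15% = 4.5%, 0.5 × 15% = 7.5%, 0.7 × 15% = 10.5%.

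**Step 2: neutropenia.** The same formula gives no fixed direction, because FOLFIRI patients are also at risk.

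| Assumed *rF*, *rI* | *w* = 0.3 | *w* = 0.5 | *w* = 0.7 | Against the FOLFOX rate |
|---|---|---|---|---|
| 15%, 0% (oxaliplatin only) | 4.5% | 7.5% | 10.5% | lower |
| 15%, 6% | 8.7% | 10.5% | 12.3% | lower |
| 20%, 20% | 20% | 20% | 20% | equal |
| 15%, 20% | 18.5% | 17.5% | 16.5% | higher |

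For example, 0.3 × 15% + 0.7 × 6% = 4.5% + 4.2% = 8.7%. The documents do not say which row applies. Protocol 7.1.5 says "Patients receiving cetuximab in combination with platinum-based chemotherapy are at increased risk of severe neutropenia" but names no comparator. Protocol 7.1.6 compares with platinum chemotherapy without cetuximab, and SAP 4.1.1 compares with 5-FU and leucovorin. None of them compares with FOLFIRI plus cetuximab, and Protocol 7.3.3 has neutropenia dose rules for FOLFIRI too.

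**Step 3: Table 14.** It covers events related to cetuximab, which is part of both regimens. The step 1 argument about unexposed patients does not apply to it.

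**Step 4: price of splitting.** Approximate 95% half-width = 1.96 × √(0.15 × 0.85 / *n*) at an assumed 15% rate. If all 221 were treated, a FOLFOX column would hold 0.3 × 221 ≈ 66 to 0.7 × 221 ≈ 155 patients, giving about 8.6 to 5.6 percentage points. One column of 221 gives about 4.7 points.

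**The case against.** The strongest reply is that the pooled tables answer the question that was asked. The trial has a single arm, its safety objective is the safety of cetuximab 500 mg/m² every two weeks, and no objective asks for safety by chemotherapy partner. That stands: the total column is legitimate and should stay. What is missing is a further presentation beside it. The reply does not remove the need for one, because the endpoint concerns events from the combination and the feasibility statement names both combinations.

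A second reply is that a reader could rescale an oxaliplatin-only rate from the regimen counts in Tables 6 and 7. This is only partly available. Table 6 is laid out by biomarker, and its BRAF columns add to 161 + 20 = 181, the efficacy set and not everyone treated. The regimen lines in Table 7 follow a line on patients with three or fewer administrations, so it is unclear whether they are totals.

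Four stronger readings are tempting, and the documents do not support them:
- A reader might infer that severe neutropenia is also under-reported for FOLFOX. Step 2 shows that this depends on a FOLFIRI rate that is not given.
- A reader might infer that every safety table is diluted by unexposed patients. Table 14 is not, and Table 11 cannot be seen.
- A reader might infer a matching understatement of irinotecan harms. The formula would apply to a harm confined to irinotecan, but this point rests on no passage that identifies one.
- A reader might infer that the feasibility conclusion fails. It also draws on PFS, OS and response.

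One limit also applies to the main point. Eligibility allows relapse after adjuvant treatment, so a FOLFIRI patient could carry neuropathy from earlier therapy. The zero rate in step 1 therefore refers to harm from oxaliplatin given in the study.

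**Conclusion.** The point holds in a limited form. None of the safety tables shown separates the regimens, and neither document plans to. For harm confined to study oxaliplatin, Tables 10, 12 and 13 will understate the FOLFOX rate by the factor *w*, the FOLFOX share. The size cannot be derived from the documents. The illustration of 15% shown as 4.5% to 10.5% rests wholly on the assumed rate and the assumed 30% to 70% share. No direction can be claimed for neutropenia, and Table 14 has no unexposed denominator.

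This is an inexpensive improvement to safety reporting. It does not touch the primary objective, the sample size or data collection.

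**What to change.** In SAP section 7, keep the total column in Tables 10, 12 and 13 and add two columns by regimen received, FOLFOX6 plus cetuximab and FOLFIRI plus cetuximab, each headed with its own number of treated patients. Do the same in Table 14 if wanted: it would show whether cetuximab-related events differ by chemotherapy partner, although the denominator argument does not require it. Add a sentence to SAP 6.5.1.4 planning this presentation, and a footnote saying that investigators chose the regimen without randomisation, so the columns describe each regimen and are not a comparison. Exact 95% confidence intervals for events of grade 3 or higher are optional.

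No new data are needed, since the chosen regimen is recorded on the inclusion form (Protocol 6.4) and appears in SAP Tables 6 and 7. The cost is revised table shells and lower precision in each regimen column, as shown in step 4.
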